- Laboratory screening orders (CBC, chemistry panel, pregnancy test, HIV status)
- Patients will be prescribed topical corticosteroid (prednisolone acetate 1%) to be used one drop in affected eye four times per day (this is typical standard of care)
- Patients requiring management of elevated IOP will be prescribed IOP-lowering medication according to treating ophthalmologist's discretion and best medical judgment

Exam 1 Randomization and Procedures

[figure not shown]
- Review of results of in- house CMV PCR and laboratory results
- Consent, enrollment, randomization to treatment arm if participants meet eligibility criteria
- Clinical eye examination (in the following order: visual acuity, slit lamp examination of anterior segment, intraocular pressure assessment, confocal microscopy)

Randomization to 1 of 3 arms

Exam 2 (Day 7) Follow-up

- Clinical eye examination (in the following order: visual acuity, slit lamp examination of anterior segment, intraocular pressure assessment)
- **Anterior chamber paracentesis #2**
- **Assessment of clinical quiescence (grading anterior chamber cell)**
- Laboratory monitoring orders (complete blood count, complete metabolic panel)

Exam 3 (Day 21) Final visit for trial I

Trial II

**Exam 1
(Re-randomization)**

Clinically inactive (< 1+ anterior chamber cell)
for at least 2 weeks with at least 2 weeks
wash-out period (no antivirals)

- Clinical eye examination (in the following order, VA, slit lamp examination of anterior segment, IOP)
- **Suppressive treatment initiation (randomized to 1 of 3 arms)**

Group 1: Oral
valganciclovir N=35

Group 2: Topical
ganciclovir 2% N=35

Group 3: Placebo
N=35

**Exam 2
(1 month after
randomization)**

- Clinical eye examination (in following order, VA, slit lamp examination of anterior segment, IOP)
- **Assessment for recurrence of inflammation**
- **Anterior chamber paracentesis #3 if recurrent inflammation (participant exits study if recurrent inflammation)**

**Exam 3
(3 months after
randomization)**

- Clinical eye examination (in following order, VA, slit lamp examination of anterior segment, IOP)
- **Assessment for recurrence of inflammation**
- Confocal or specular microscopy if recurrent
- **Anterior chamber paracentesis #3 if recurrent inflammation (participant exits study if recurrent inflammation)**

**Exam 4
(5 months after
randomization)**

- Clinical eye examination (in following order, VA, slit lamp examination of anterior segment, IOP)

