Primary analysis for Trial II. The primary outcome for Trial II is recurrence of inflammation (≥ 1 +anterior chamber cell) over 12 months. We calculated the effect size we would be able to observe with 80% power, a two-sided alpha of 0.05/2, and 28 participants per arm (105 total from Trial I with 20% loss to follow-up) based on a two-sample z-test for proportions. Assuming the risk of recurrence is 25% in the placebo group, we can detect a difference of 36 percentage points between the oral valganciclovir and the placebo groups. We acknowledge that having fewer recurrences in the placebo group compared to oral antiviral group may be contradictory to what one might think would typically occur with exposure to antivirals. However, it is well documented in the literature that long-term suppressive-level dosing of antiviral in an immunodeficient host or in an immunologically privileged organ (such as the eye) can create an environment permissive to the development of antiviral resistance.^{13-15,18,20}

For Specific Aim 3, we estimated the minimum detectable effect for the difference in prevalence of infections that have antiviral resistance mutations among recurrent infections in Trial II among patients who receive long-term antiviral prophylaxis compared with their infections at baseline. Aim 3 will focus on patients in the two active treatment arms in Trial II, because we would expect long-term use of topical and oral antivirals to lead to similar selection for antiviral resistance. From 117 participants enrolled, we conservatively assumed that 72% of patients would complete both Trial I and Trial II (n=84). We further assumed that 60% of patients will develop a recurrent infection over the monitoring period during the trials (Table 1)⁷. Participants who receive active treatment in Trial II (treatment regimens C+D) will contribute to the Aim 3 analysis (n=34). The analysis will be a paired analysis, comparing the proportion of recurrent infections with antiviral resistance mutations with that same proportion at baseline. *Please refer to the Statistical Analysis Plan (SAP) for further details.*

Randomization

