**Primary analysis for Trial II.** The primary outcome for Trial II is the proportion of participants experiencing CMV recurrence over 12 months. We acknowledge that hypothesizing fewer recurrences in the placebo group compared to the oral antiviral group is contradictory to what one might think would typically occur with exposure to antivirals. However, data from a previous observational study showed a one-year recurrence risk of 25.0% (3/12) among participants who did not receive antiviral treatment and 75.0% (9/12) in participants receiving systemic antiviral treatment (oral ganciclovir or valganciclovir), which is similar to the experience of other research. Additionally, it is well documented that long-term suppressive-level dosing of antiviral in an immunodeficient host or in an immunologically privileged organ (such as the eye) can create an environment permissive to the development of antiviral resistance. Given 28 participants per arm (105 total from Trial I with 20% loss to follow-up) and a recurrence risk of 25% in the placebo group, we can detect a difference of 40 percentage points between the oral valganciclovir and the placebo groups (from 25% to 65%), using a two-sample z-test for proportions with 80% power and a two-sided alpha of 0.05/2.

**For Specific Aim 3,** we estimated the minimum detectable effect for the difference in prevalence of infections that have antiviral resistance mutations among recurrent infections in Trial II among patients who receive long-term antiviral prophylaxis compared with their infections at baseline. Aim 3 will focus on patients in the two active treatment arms in Trial II, because we would expect long-term use of topical and oral antivirals to lead to similar selection for antiviral resistance. From 117 patients enrolled, we conservatively assumed that 72% of patients would complete both Trial I and Trial II (n=84). We further assumed that 60% of patients will develop a recurrent infection over the monitoring period during the trials (Table 1). Participants who receive active treatment in Trial II (treatment regimens C+D) will contribute to the Aim 3 analysis (n=34). The analysis will be a paired analysis, comparing the proportion of recurrent infections with antiviral resistance mutations with that same proportion at baseline.

Table 1. Anticipated participant enrollment, and follow-up by treatment patterns

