## 6. Analysis

### 6.1. Outcome definitions

Trial I: Primary Endpoint: Log-transformed viral load after 7 days of treatment

Secondary Endpoints:

- Anterior chamber cell (days 7, 21)
- Intraocular pressure (days 7, 21)
- Visual acuity (days 7, 21)
- Controlled inactivity defined as  $\leq 0.5+$  anterior chamber cell AND intraocular pressure  $< 24$  mmHg AND no cornea edema AND no active KPs (day 7, 21).

Trial II: Primary Endpoint: Proportion recurrent inflammation ( $\geq 1+$  anterior chamber cell at any study visit) over 12 months

Secondary Endpoints:

- Prevalence of CMV associated with recurrence of uveitis

1a. The Aim 1 primary outcome **viral load after 7 days of treatment** will use the results from quantitative PCR at 7 days of treatment or placebo therapy (day 7 of trial). All quantitative PCR viral loads will undergo base-10 logarithm-transformation, with units converting from IU/mL to log IU/mL. Log-transformed viral loads will be used because the range of viral loads can be wide and dealing with very large and very small numbers is handled more efficiently using a logarithmic scale. Such normalization of the distribution of viral loads is consistent with standard practice in viral load analyses.

1b. **Clinical outcomes and inactivity:** At each study visit participants will be clinically examined for ocular outcomes including AC inflammatory cells, intraocular pressure, and visual acuity. A study ophthalmologist will make a clinical determination as to whether the patient's inflammation is considered inactive. Clinical outcomes and the proportion of participants that

achieve quiescence by day 7 and 21 will be compared by arm. Patients will also be administered a questionnaire querying when they felt symptomatic improvement in their condition. This analysis will be viewed as hypothesis generating and will be treated as supplementary and in addition to the main finding.

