### Primary Analysis Trial II

**Aim 2a. Recurrence rate of anterior uveitis over 12 months:** The proposed analysis for sub-Aim 2a (Trial II), which is a clinical outcome, is a log-binomial regression model to compare cumulative inflammatory recurrence (based on anterior chamber cell  $\geq 1+$  cell) between treatment groups. We will censor participants at the first recurrence of anterior uveitis (based on anterior chamber cell  $\geq 1+$  cell) or 12 months. The model includes indicators for the treatment arm and indicators for each site used to stratify the randomization. We will estimate the risk ratios from the model for the two primary comparisons, *oral valganciclovir* vs. *topical ganciclovir 2%*, and *oral valganciclovir* vs. *placebo*. We will use a simulation-based permutation test to estimate p-values, and will report max-T simultaneous confidence intervals and p-values adjusted for the two pair-wise comparisons (*oral valganciclovir* vs. *topical ganciclovir 2%*, *oral valganciclovir* vs. *placebo*). Pre-specified sub-group analyses by sex will be performed.

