### Sensitivity Analyses

In all analyses, model adequacy will be checked by examination of residuals or other goodness of fit tests as needed. Inadequate model fit will prompt us to report alternative models. If there are chance imbalances in prognostic baseline patient characteristics, including age, sex, and prednisolone use prior to enrollment, a secondary analysis will include them as covariates in the regression model.

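### Trial II primary model (Aim 2a) adjusts for site only; prespecifying entry anterior chamber cell grade (0 v 0.5+) would be a cheap efficiency gain of uncertain size

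*SAP*

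**What the plan says.** The Aim 2a model is a log-binomial regression for cumulative recurrence. On covariates the SAP (6.2, Primary Analysis Trial II) says: "The model includes indicators for the treatment arm and indicators for each site used to stratify the randomization". P-values come from a simulation-based permutation test with max-T adjustment.

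The Protocol schema describes Trial II entrants as "Clinically inactive (< 1+ anterior chamber cell"), sustained for at least 2 weeks. Protocol 8.3 and SAP 6.1 put inactivity at 0.5+ or below, so entrants are at grade 0 or 0.5+. The endpoint is on the same scale: 1+ or more "anterior chamber cell at any study visit) over 12 months" (SAP 6.1).

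Entry grade will exist for everyone. The eye examination form is completed at Trial II Exam 1 (Protocol 1.2 and 7.1.3), and the slit lamp examination covers anterior chamber cell (Protocol 7.1.1). This includes patients who enter Trial II directly and may have no Trial I viral load.

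The only other covariate provision is under Sensitivity Analyses in SAP 6.2: "If there are chance imbalances in prognostic baseline patient characteristics", with age, sex and prior prednisolone use given as examples, a secondary analysis adds them to the model.

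Trial I is handled differently. Its primary model includes baseline viral load, and its sample size relies on the precision this brings (SAP 3.3).

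**The concern.** Trial I uses the baseline value of its endpoint measure and Trial II does not, although Trial II has fewer evaluable participants and is sized at 80% power with no margin at its stated difference. A participant entering at 0.5+ is one grade below the recurrence threshold, while one entering at 0 is two grades below. If that distance predicts recurrence, leaving grade out costs some precision. Randomisation is stratified by site only, so nothing in the design balances entry grade between arms. A covariate brought in only after an imbalance is seen, and only in a secondary analysis, serves less well than one named in advance. The stake is a few points of power and some protection against chance imbalance, not validity.

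**Working it through.** **Inputs from the documents.** All are in SAP 3.3, Trial II paragraph:
- evaluable per arm: 105 × 0.8 / 3 = 28
- assumed recurrence: 25% on placebo and 65% on oral valganciclovir, a gap of 40 points
- test and error rates: "using a two-sample z-test for proportions with 80% power and a two-sided alpha of 0.05/2"

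**Reproducing the plan's figure.** Pooled two-sided z-test:

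power = Φ{[d√n − z√(2p̄(1−p̄))] / √(p₁(1−p₁)+p₂(1−p₂))}

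With n = 28, d = 0.40, p̄ = 0.45 and z = 2.241:
- numerator: 0.40 × 5.292 − 2.241 × 0.7036 = 2.117 − 1.577 = 0.540
- denominator: √(0.1875 + 0.2275) = 0.644
- power = Φ(0.838) = 79.9%

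The SAP figure reproduces. Protocol 8.2 states, for the same n, alpha and power, "we can detect a difference of 36 percentage points between the oral valganciclovir and the placebo groups". That does not reproduce: 25% v 61% has 69.7% power at 28 per arm, and 80.5% at 35 per arm. The two documents need reconciling, but this is a separate matter.

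**Assumptions, absent from the documents.** q is the share entering at 0.5+, taken as 20-50%. OR is the odds ratio for recurrence, 0.5+ v 0, equal in both arms, taken as 1, 2, 4 and 6. Marginal risks stay at 25% and 65%. Site is left out of both analyses compared.

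**One setting by hand (q = 0.5, OR = 4).** The risks by grade that average to 25% and 65% are:
- placebo: 0.129 at grade 0 and 0.371 at 0.5+ (odds 0.148 and 0.590)
- oral valganciclovir: 0.500 and 0.800 (odds 1 and 4)

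Variance of the risk difference, multiplied by n:
- unadjusted: 0.1875 + 0.2275 = 0.415
- adjusted and standardised: mean within-grade variance in each arm, plus half the variance of the grade-specific risk difference
  - placebo: (0.1124 + 0.2334)/2 = 0.173
  - oral: (0.250 + 0.160)/2 = 0.205
  - third term: ½ × 0.25 × (0.429 − 0.371)² = 0.0004
  - total: 0.378

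The ratio is 0.378/0.415 = 0.911, so effective n = 28/0.911 = 30.7. Power = Φ[(0.40 × √30.7 − 1.577)/0.644] ≈ 84%, a gain of about 4 points over 79.9%.

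**By simulation.** Pooled z-test v a test stratified by entry grade (Cochran-Mantel-Haenszel), 28 per arm, alpha 0.025, q from 20% to 50%. Unadjusted power is about 79%.

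| OR, 0.5+ v 0 | Gain in power (points) |
|---|---|
| 1 | 0 |
| 2 | about 1 |
| 4 | about 3-4 |
| 6 | about 4-7 |

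Type I error is at or below about 2.5% with and without adjustment.

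**On a risk-ratio scale.** With a constant risk ratio in both arms, the gain is at most about 1.7 points at a ratio of 1.5 or less, about 5 points at 2 (q 35-50%), and 8-11 points only at 2.5-3 with half of participants at 0.5+.

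**Chance imbalance.** The between-arm difference in the share at 0.5+ has SD √(2q(1−q)/28), which is 0.122 at q = 0.3 and 0.134 at q = 0.5. At q = 0.5 and OR = 4 the mean risk gap between grades is (0.242 + 0.300)/2 = 0.271. A one-SD imbalance therefore moves the unadjusted risk difference by 0.134 × 0.271 = 0.036, about 3.5 points.

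**The case against.** The strongest reply is that the planned comparison is valid: it adjusts for the only stratification factor, and covariate choice is a matter of discretion. That stands. A reader might infer that the plan is biased, or that it demonstrably gives away power. The documents support neither. They do not show that entry grade predicts recurrence. The covariate spans two adjacent grades, entrants must have been inactive for at least 2 weeks, and the endpoint runs for 12 months, so its predictive strength could be small. In the placebo arm, with 30-50% at 0.5+, an odds ratio of 4 means a risk ratio of 2.7-2.9 and an odds ratio of 6 means 3.5-4.0. These are strong effects.

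A reader might also infer that no correction for imbalance in entry grade is planned. The Sensitivity Analyses list is open-ended, so entry grade could be added. But that route is secondary, has no stated threshold, and does not name entry grade.

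Nor is Trial II necessarily short of power. SAP 3.3 cites observed one-year recurrence of 3/12 v 9/12. At 25% v 75% the same formula gives Φ[(0.50 × 5.292 − 2.241 × 0.7071)/0.612] ≈ 96%. With 12 per group that prior is fragile. Direct entry to Trial II could also raise numbers above 28 per arm.

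The practical objection has force. With about 84 completers and six sites, log-binomial fits are fragile. In simulations with assumed unequal site sizes and a plain fitter, 62-68% failed to converge or left the valid range without entry grade, and 77-82% with it. Those rates depend on the assumptions, but the direction means that the term should not simply be added to the log-binomial model. Finally, the simulated gains compare simpler tests than the planned permutation and max-T procedure, so they indicate the scale and are not exact.

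**Conclusion.** The point holds as an efficiency improvement, not as an error. The Aim 2a model omits a baseline measure that every entrant has and that lies on the endpoint's own scale, while Trial I adjusts for its equivalent. The benefit ranges from nothing, if entry grade is not prognostic, to about 3-4 points of power at an odds ratio of 4 and 4-7 at 6. This rests on 20-50% entering at 0.5+ and an equal odds ratio in both arms, neither of which the documents give. No loss of power or type I error inflation appeared when entry grade was uninformative. It is worth doing because the cost is small, not because the gain is assured.

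**What to change.** Before any unmasked Trial II comparison, amend SAP 6.2 as follows.

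1. Name entry anterior chamber cell grade (0 v 0.5+, from Trial II Exam 1) as a prespecified covariate, with arm and site, in the Aim 2a primary model and the Aim 2c Cox model.
2. For Aim 2a, replace the plain log-binomial fit with a logistic working model. Obtain the risk ratio and risk difference by standardising predictions over the sample. Aim 1b already uses marginal predictions, and the risk difference would meet the absolute-scale reporting promised in SAP 4.1.
3. Base the planned permutation test on that adjusted statistic, permuting arm within site, and keep the max-T adjustment for the two comparisons.

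The cost is one model term and a short description of the estimator. No new data, visits or participants are needed.

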### Secondary Analyses Trial II

**Aim 2b. Prevalence of detectable CMV with recurrence.** The proposed outcome for Aim 2b is prevalence of detectable CMV (CMV positive) based on nucleic acid amplification testing obtained from anterior chamber fluid (aqueous humor) obtained at recurrence during Trial II. Thus, this sub-aim is a microbiologic outcome. We will calculate the proportion of recurrence episodes with detectable CMV viral load by using log-binomial regression with treatment arm indicators and site stratification. We will report adjusted confidence intervals and p-values for treatment arm comparisons. For correlation between viral load and inflammation, we will assess the relationship between log-transformed viral load and anterior chamber cell grade at recurrence of inflammation using a log-binomial regression model adjusting for treatment arm and site. Pre-specified subgroup analyses by sex will be performed for both components. We will handle missing data through sensitivity analyses using multiple imputation.

**Aim 2c. Time to first CMV anterior uveitis recurrence within 12 months.** An exploratory outcome of Trial II will be the time to first CMV anterior uveitis recurrence within 12 months. We will use a Cox proportional hazards model to compare the time to recurrence by the arm within the 12 months of long-term suppressive therapy, including an indicator for each treatment arm and an indicator for site. We will assess the proportional hazards assumption by examining Kaplan-Meier curves by treatment group on the original and log-log scales and will examine Schoenfeld residuals to assess model fit. We will estimate the hazard ratio from the model for the two primary comparisons, *oral valganciclovir* vs. *topical ganciclovir 2%*, *oral valganciclovir* vs. *placebo*. Both comparisons will use max-T adjusted p-values and simultaneous 95% confidence intervals. Sensitivity analyses will examine 1) alternative censoring assumptions and 2) time-varying hazards if proportional hazards assumption is violated.

**Aim 3. Prevalence of mutations conferring antiviral resistance:** The analysis population will include individuals enrolled in both Trials I and II who are randomized to receive oral or topical antivirals in Trial II and experience a recurrent infection. Among patients that experience a recurrent infection (anticipated n=34, see Sample Size section 3.3), we will compare the proportion of infections with antiviral mutations upon recurrence with the proportion with antiviral mutations at baseline. The analysis will thus be a pair-matched analysis (within-patient). We will use a linear binomial model to estimate the difference in prevalence of resistant infections, including fixed effects for each participant that will control for all between-participant characteristics in this observational analysis. Additional covariates in the model will include treatment arm and site. This pair-matched analysis is similar to McNemar's test, but allows us to control for type of retroviral and enrollment site using regression.

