**2a. Proportion recurrent inflammation over 12 months:** After achieving clinical quiescence, participants will be offered enrollment in Trial II where they would be randomized to long-term suppressive therapy to study the effect on recurrence rate of anterior uveitis. Each participant will be assessed for recurrence at each monthly visit during the 12 months or, alternatively, if participant's experience symptoms of a recurrence, then they will be instructed to call the local site's clinical coordinator to be scheduled for an evaluation within 1 to 2 days. Recurrence of uveitis in CMV is mostly typically symptomatic, so having participants call us is expected to be an effective strategy for catching recurrence of uveitis. If recurrence occurs, aqueous chamber fluid will be collected from participant at the time of recurrence to quantify viral load.

**2b. Prevalence of CMV associated with recurrence of uveitis:** Aqueous fluid obtained in participants exhibiting recurrence of uveitis during Trial II will be submitted for directed polymerase chain reaction testing to determine the proportion of uveitis flares associated with CMV (as compared to “sterile” inflammation).

**3a. Prevalence of mutations conferring antiviral resistance:** The analysis population will include individuals enrolled in both Trials I and II who are randomized to receive oral or topical antivirals in Trial II and experience a recurrent infection. Among patients that experience a recurrent infection (anticipated n=34, see Sample Size section 3.3), we will compare the proportion of infections with antiviral mutations upon recurrence with the proportion with antiviral mutations at baseline.

**3b. Pathogens other than CMV and host transcriptional profile:** (i) In aqueous we will describe the host transcriptional profile in participants with CMV anterior uveitis entering Trial I and in those who fail to enter Trial I due to having negative CMV PCR testing. (ii) We will identify and describe non-CMV pathogens in cases unable to enter Trial I. (iii) We will describe host transcriptional profile in participants during Trial II who have recurrent inflammation.

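### Aim 2b tests arms on CMV detection only among participants who recurred, a non-randomised subset, and no analysis clearly defines the randomised effect on CMV-positive recurrence

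*SAP*

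**What the plan says.** SAP 6.1 lists one secondary endpoint for Trial II: "Prevalence of CMV associated with recurrence of uveitis". Item 2b there describes its purpose, which is to test aqueous from flares "to determine the proportion of uveitis flares associated with CMV" as opposed to sterile inflammation. That is a descriptive aim.

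SAP 6.2, Secondary Analyses Trial II, turns it into a treatment comparison. The outcome is CMV detection in samples "obtained from anterior chamber fluid (aqueous humor) obtained at recurrence during Trial II". The model is specified as "We will calculate the proportion of recurrence episodes with detectable CMV viral load by using log-binomial regression with treatment arm indicators", followed by "We will report adjusted confidence intervals and p-values for treatment arm comparisons".

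Two design features fix the denominator:
- Sampling depends on recurrence (SAP 6.1, item 2a): "If recurrence occurs, aqueous chamber fluid will be collected from participant at the time of recurrence to quantify viral load".
- The Protocol synopsis adds at each Trial II follow-up visit: "participant exits study if recurrent inflammation". There is therefore at most one episode per participant.

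On the recurrence outcome itself, SAP 6.1 and Aim 2a define it by anterior chamber cell of 1+ or more, with no CMV requirement. SAP 3.3 labels it differently: "The primary outcome for Trial II is the proportion of participants experiencing CMV recurrence over 12 months". Aim 2c is titled as time to a first CMV anterior uveitis event, but its Cox model is then described simply as time to recurrence.

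**The concern.** Whether a participant enters the Aim 2b comparison is decided after randomisation, by the Trial II primary outcome. SAP 2.2 hypothesises that this outcome differs by arm, with fewer recurrences on placebo. Participants who flare on valganciclovir and those who flare on placebo may differ in prognosis and in the nature of the flare, and randomisation no longer balances them. The SAP calls its other analysis of recurrers, Aim 3, observational. Aim 2b carries no such caution.

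The question matters for this trial because the sponsor's rationale is that long-term antiviral exposure may increase recurrence through resistance. A direct check is whether more participants on antiviral have a recurrence with CMV present. The share of flares that are CMV-positive does not answer that, and it can move in the opposite direction. A reader who sees a lower CMV share on valganciclovir, with a p-value, could take it as a virological benefit while more valganciclovir participants have CMV-positive recurrences.

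**Working it through.** **Inputs from the documents.** Placebo recurrence risk 25%, detectable oral risk 65%, 28 per arm after 20% loss, two-sided alpha 0.025, 80% power (SAP 3.3). Loss: 105/3 = 35 per arm, and 35 × 0.8 = 28. Aim 2b has no power figure of its own.

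**Inputs assumed.** The CMV-positive fraction of recurrences by arm is not given, so a range of 30% to 90% is used.

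**1. Reproduce the SAP figure.** Two-sample z-test with pooled variance under the null, mean risk 0.45:

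z = [0.40 × √28 − 2.241 × √(2 × 0.45 × 0.55)] / √(0.25 × 0.75 + 0.65 × 0.35) = (2.117 − 1.577) / 0.644 = 0.84, so power is 0.799. The 40-point difference reproduces.

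**2. Link the two contrasts.** With one episode per participant:

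P(CMV-positive first recurrence) = P(recurrence) × P(CMV-positive given recurrence)

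Hence RR(all randomised) = RR(recurrence) × RR(CMV-positive among recurrers). At 65% v 25%, RR(recurrence) = 0.65/0.25 = 2.6. The two contrasts have opposite signs when the ratio among recurrers lies between 1/2.6 = 0.385 and 1.

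**3. Put numbers in** (oral first, then placebo).

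| Recurrence risk | Assumed CMV-positive fraction | RR as in Aim 2b | Risk among all randomised | RR, all randomised |
|---|---|---|---|---|
| 65%, 25% | 50%, 80% | 0.63 | 32.5%, 20.0% | 1.63 |
| 65%, 25% | 60%, 90% | 0.67 | 39.0%, 22.5% | 1.73 |
| 65%, 25% | 40%, 75% | 0.53 | 26.0%, 18.8% | 1.39 |
| 65%, 25% | 90%, 90% | 1.00 | 58.5%, 22.5% | 2.60 |
| 65%, 25% | 90%, 60% | 1.50 | 58.5%, 15.0% | 3.90 |
| 65%, 25% | 30%, 90% | 0.33 | 19.5%, 22.5% | 0.87 |
| 40%, 60% (assumed) | 90%, 75% | 1.20 | 36.0%, 45.0% | 0.80 |

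The first three rows reverse. The fourth shows no difference in Aim 2b despite a 2.6-fold difference among all randomised. Rows five and six agree in sign. The last row shows that reversal can also occur if antivirals reduce recurrence.

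**4. Size of the subset.** At 28 per arm, expected recurrences are 28 × 0.65 = 18.2 on oral and 28 × 0.25 = 7.0 on placebo. For 60% v 90% CMV-positive, approximate power at two-sided 0.025 is about 16% (normal approximation, rough with 7 in one arm).

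**5. Exits with a CMV-negative flare.** In the first row, 0.65 × 0.5 = 32.5% of oral and 0.25 × 0.2 = 5% of placebo participants leave after a CMV-negative flare. Any later CMV flare in them is unobserved, so the replacement endpoint has to be worded as the first recurrence.

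**The case against.** Four arguments on the other side have force.

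- **Flares are the right denominator for the stated question.** Asking whether recurrences are viral or sterile does call for a proportion of flares. This stands, but it supports a descriptive proportion, not p-values between arms.
- **Aim 2c may already cover the randomised effect.** A reader might infer that no analysis estimates the effect on CMV recurrence. The documents do not support so flat a statement. Aim 2c names such an event, compares it by arm and is not restricted to recurrers. If the event means PCR-positive recurrence, Aim 2c is an exploratory estimate of that effect. But it gives no PCR criterion and no rule for CMV-negative flares, and SAP 3.3 uses similar wording for the cell-grade outcome, so the event is undefined.
- **Reversal rests on assumed fractions.** It requires lower CMV positivity on oral at the SAP's 65% v 25%. Hypothesis 2b expects virus to be detectable at recurrence, and the resistance rationale gives no particular reason for fewer viral flares on antiviral. This stands: reversal is possible, not predicted.
- **The consequence is limited.** Aim 2b is not among the key secondary endpoints in SAP 4.1. Multiplying the Aim 2a risk by the Aim 2b proportion also gives an unadjusted point estimate of the missing quantity. Both are true, but the SAP does not plan that product, and it would come without an interval or test.

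**Conclusion.** The point holds as an improvement that should be made, not as a threat to the primary analysis. Aim 2b attaches p-values to a comparison within a subset selected by the primary outcome, and SAP 6.2 does not mark it as non-randomised. At the SAP's 65% v 25%, it would point the opposite way to the all-randomised contrast for any ratio among recurrers between 0.385 and 1. That interval depends on the 2.6 risk ratio, which is a detectable difference in SAP 3.3 and not a forecast. Where the trial would fall within or outside the interval cannot be derived from the documents. The figures concern oral v placebo; SAP 3.3 gives no topical recurrence risk.

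Two further inferences are not supported. CMV-positive recurrence will not be known for every randomised participant: it will be missing for dropouts and for flares without a usable sample, and it is unobserved after a CMV-negative flare ends participation. Nor is the primary endpoint itself undefined: SAP 6.1 and Aim 2a both define it by cell grade, and the SAP 3.3 label is loose wording.

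**What to change.** In SAP 6.1 and 6.2:

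- Report the proportion of flares that are CMV-positive by arm descriptively, without arm p-values.
- Make the Aim 2b arm comparison a first recurrence (1+ cell or more) by 12 months with detectable CMV in the recurrence aqueous. Use all randomised participants as the denominator (planned 35 per arm, about 28 with outcome data), Aim 2a's contrasts and site adjustment, and the SAP 6.3 missing-data approach for dropouts.
- State that a CMV-negative first flare counts as a non-event that ends observation, that is, a competing event, and report its frequency by arm.
- Add a sensitivity analysis for recurrences without a usable aqueous sample.
- State in Aim 2c whether the event is any recurrence of inflammation or a PCR-positive recurrence. If the latter, treat CMV-negative flares as a competing event.

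In SAP 3.3, word the primary outcome as recurrence of inflammation, to match SAP 6.1.

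The cost is SAP wording and one extra model, with no new data collection. The downside is that the estimand is limited to the first flare.
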